Provide a statement that the trial will be conducted in compliance with the protocol, International Council on Harmonisation Good Clinical Practice (ICH GCP) and applicable state, local and federal regulatory requirements. Each engaged institution must have a current Federal-Wide Assurance (FWA) issued by the Office for Human Research Protections (OHRP) and must provide this protocol and the associated informed consent documents and recruitment materials for review and approval by an appropriate Institutional Review Board (IRB) or Ethics Committee (EC) registered with OHRP. Any amendments to the protocol or consent materials must also be approved before implementation. Select one of the two statements below. If the study is an **intramural** NIH study, use the second statement below:

- 1. The trial will be carried out in accordance with International Council on Harmonisation Good Clinical Practice (ICH GCP) and the following:
 - United States (US) Code of Federal Regulations (CFR) applicable to clinical studies (45 CFR Part 46, 21 CFR Part 50, 21 CFR Part 56, 21 CFR Part 312, and/or 21 CFR Part 812).

National Institutes of Health (NIH)-funded investigators and clinical trial site staff who are responsible for the conduct, management, or oversight of NIH-funded clinical trials have completed Human Subjects Protection and ICH GCP Training.

OR

2. The trial will be conducted in accordance with International Council on Harmonisation Good Clinical Practice (ICH GCP), applicable United States (US) Code of Federal Regulations (CFR), and the [specify NIH Institute or Center (IC) [Terms and Conditions of Award. The Principal Investigator will assure that no deviation from, or changes to the protocol will take place without prior agreement from the funding agency and documented approval from the Institutional Review Board (IRB), and the Investigational New Drug (IND) or Investigational Device Exemption (IDE) sponsor, if applicable, except where necessary to eliminate an immediate hazard(s) to the trial participants. All personnel involved in the conduct of this study have completed Human Subjects Protection and ICH GCP Training.

For either option above, the following paragraph would be included:

1 PROTOCOL SUMMARY

1.1 SYNOPSIS

Title: Word Retrieval in the Wild: An Ecological Momentary

Assessment Pilot Study in People with Post-Stroke Aphasia

Grant Number: UL1 TR002544

Study Description: People with post-stroke aphasia (PWA) suffer from anomia, a condition

where they know what they want to

say but cannot retrieve the words. For PWA, word retrieval changes

moment-to-moment, leading to diminished

motivation to participate in conversations and disengagement from

social interactions. In the real world, anomia

variability and severity are compounded by contextual factors of

communication exchanges (noise, dual-tasking).

Ecological momentary assessment (EMA) involves in-situ measurement

of a behavior over time during everyday

life. EMA has promise for capturing real-world anomia, yet EMA

methods have not been tested in PWA.

To target in-situ anomia, PWA will complete 36 picture-naming

trials/day for three weeks,

delivered either as a single trial 36 times per day (1-item EMA condition) or in four sets of nine trials/set per day (9-item EMA condition). Prior to completing community/home-based EMAs, participants will undergo standardized testing and smart device training. During the EMA period, participants will complete a brief survey about their EMA experiences at the end of each week. Following completion of the EMA protocol, participants will complete one final

assessment and exit interview session.

Objectives*: Primary Objective: To evaluate the feasibility of ecological

momentary assessment (EMA) of naming abilities in people with post-stroke aphasia

Secondary Determine relationships between feasibility

Objectives: metrics and personal factors

Endpoints*: Primary Endpoint: Compliance and completion over a 3-week

EMA protocol

Secondary Perceived burden of completing EMAs

Endpoints: during the 3-week protocol

Study Population: Individuals with post-stroke aphasia

Phase* or Stage: Chronic stroke (at least 6 months after stroke onset)

Description of Sites/Facilities Enrolling Participants:

Participants will be recruited through The Aphasia Network (TAN) Lab at Northeastern University.

[figure not shown]
Description of Study Manipulation:

Following consent and prior to completing community/home-based Intervention/Experimental EMAs, participants will undergo standardized testing and smart device training. PWA will be pseudorandomly assigned to either the 1-item or 9-item EMA condition, counterbalanced for aphasia severity. Next, PWA will complete the three-week community/home-based EMA protocol. Each day, PWA will be scheduled to attempt naming aloud 36 pictures that appear on the smartwatch, either delivered either as a single trial 36 times per day (1-item EMA condition) or in four sets of nine trials/set per day (9-item EMA condition). During the EMA period, participants will complete a brief survey about their EMA experiences at the end of each week. Following completion of the EMA protocol, participants will complete one final assessment and exit interview session.

Study Duration*: 1 year **Participant Duration:** 5-6 weeks

1.2 SCHEMA

Figure 1. Study Design

1.3 SCHEDULE OF ACTIVITIES

Study Phase	Activities
-------------	------------

Pre-EMA Testing

Testing: (1) Quick Aphasia Battery (QAB) to measure overall aphasia severity, (2) the Pattern Comparison Processing Speed Test and Flanker Inhibitory Control and Attention Test from the NIH Cognition Toolbox to measure non-linguistic visual attention and executive functions, respectively, (3) brief, standardized picture description and story elicitation tasks to index anomia in discourse, and (4) an overt object naming test to index word retrieval via a standard SLP assessment format (i.e., single administration in a quiet 1:1 interaction). The naming test will include normed real photos17 of the 260 items from the Snodgrass and Vanderwart stimuli set. PWA will also participate in an intake interview and complete a questionnaire about their comfort with technology, adapted for aphasia (simple language, short phrases).

Smart device training including: (1) Smartwatch Orientation: PWA will be oriented to the smartwatch (interface, charging, etc.) through simple verbal and written instructions and visual demonstrations. (2) EMA Task Training: PWA will be instructed on the specific EMA naming task, including instructions on how to tap on the screen and the optimal approach for providing verbal responses (i.e., mouth close to the watch). Then, PWA will complete an 18-item traditional EMA-style naming task probe (i.e., several trials back-to-back on the smartwatch) in a quiet room in The Aphasia Network (TAN) Lab at Northeastern University. During this probe, SLP graduate student research assistants (RAs) will provide cueing and feedback so that PWA successfully learn how to operate the smartwatch and respond to prompts. (3) EMA Protocol Simulation: PWA will complete a "real-world" EMA task probe in a distracting environment (i.e., coffee shop or university bookstore on Northeastern's campus). For this final activity, over a 45-minute period, 18 smartwatch prompts will be given, either randomly interspersed with one naming trial per prompt (for PWA in the 1-item condition) or split into two sets of 9 trials per prompt (for PWA in the 9item EMA condition). This final activity will mirror the threeweek EMA protocol.

EMA Protocol

For three weeks, PWA will name aloud pictures that appear on the smartwatch as they go about their daily activities. At the end of each week, PWA will complete a virtual check-in with the study team at which time they will also complete a brief (16-item) Qualtrics survey about their EMA experiences that week.

Version 1.000

Protocol 15 March 2022

Post-EMA Protocol Testing	In a final session, PWA will complete the overt object
and Exit Interview	naming test in standard SLP format once more. Finally,
	they will participate in an exit interview about the study.

2 INTRODUCTION

2.1 STUDY RATIONALE

Ecological momentary assessment (EMA) holds promise for providing objective insight into the everyday experiences of patients with a variety of clinical conditions. To date, there is little EMA research that includes stroke survivors with aphasia. Thus, the primary rationale for this study is to evaluate and demonstrate the feasibility of a novel smartwatch-delivered, audio-based EMA of naming protocol in individuals with chronic aphasia. This project is an important first step towards testing the clinical utility of EMA for better understanding everyday communication difficulties and other challenges that PWA face in daily life.

2.2 BACKGROUND

Impaired word retrieval—also known as anomia—is one of the most debilitating symptoms stroke survivors with aphasia, a communication disorder characterized by impaired language, face in their daily lives. Like "tip-of- the-tongue" states experienced by neurotypical individuals, anomic moments in people with aphasia (PWA) occur when an individual knows what they want to say but cannot retrieve the word. Unlike "tip-of-the-tongue," anomia in PWA pervades communication exchanges and is characterized by inconsistent ability to retrieve a given word across attempts. The severity and unpredictability of anomia lead many PWA to disengage from conversation and social situations, which can severely impact their participation and quality of life. In daily life, anomia can be further compounded by real-world communication contexts such as attempting to communicate in distracting settings (e.g., with background noise and/or other people in the vicinity) or when completing other tasks. In clinical practice, speech-language pathologists (SLPs) typically assess anomia by administering a standardized test once to a patient in a quiet room. This approach captures neither the variability typical of post-stroke anomia nor the realities of real-world communication. In contrast, ecological momentary assessment (EMA) is a method often used in health research to measure physical, mental, or cognitive states in a person's daily life over several days, weeks or even months. Traditional EMA involves a device prompting a participant to answer a set of questions a few times a day, whereas micro-interactionbased EMA (µEMA) uses single-question, "at-a-glance" prompts that are interspersed over time rather than grouped into sets. Our pilot studies demonstrate that µEMA has higher response rates and lower perceived burden than traditional EMA in neurotypical individuals despite its higher interruption rate. Thus, we propose that EMA—particularly µEMA—is a viable approach to capture real-world anomia in PWAs' daily lives. Yet, despite the increasing use of technology-based assessments and therapy platforms for PWA, neither EMA nor µEMA methods have been utilized in aphasia.

Version 1.000

Protocol 15 March 2022

2.3 RISK/BENEFIT ASSESSMENT

2.3.1 KNOWN POTENTIAL RISKS

There are no known risks of ecological momentary assessment (EMA).

2.3.2 KNOWN POTENTIAL BENEFITS

There are no direct benefits as EMA is an assessment, not treatment method. Some participants may find completing the protocol engaging.

2.3.3 ASSESSMENT OF POTENTIAL RISKS AND BENEFITS

The risks do not outweigh any potential benefits.

[figure not shown]
3 OBJECTIVES AND ENDPOINTS

OBJECTIVES	ENDPOINTS	JUSTIFICATION FOR ENDPOINTS	PUTATIVE MECHANISMS OF ACTION
Primary			
Assess EMA compliance in PWA	Compliance will be calculated by dividing the number of answered prompts by the number of scheduled prompts	This metric is often used in describing feasibility of EMA protocols.	N/A - not an intervention
Assess EMA completion in PWA	Completion will be calculated by dividing the number of answered prompts by the number of	Compliance reflects protocol adherence excluding trials missed due to the watch being off/uncharged or a problem with the trial	
	delivered prompts	flow.	
Secondary			
Assess speech intelligibility of EMAs	Recorded responses will be tagged as fully intelligible (1) or partially or completely unintelligible (0)	Speech EMA requires intelligible responses to be clinically useful	N/A - not an intervention
Assess perceived burden from EMAs in PWA	Perceived burden will be calculated by averaging Likert ratings from the Qualtrics survey questions regarding perceived burden	Gathering information about participants experiences with a novel protocol is important for establishing its clinical utility	N/A - not an intervention
Tertiary/Exploratory			
Determine relationships between EMA feasibility metrics and personal factors	N/A	No explicit endpoint are applicable for this objective	N/A - not an intervention

4 STUDY DESIGN

4.1 OVERALL DESIGN

Figure 1. Study Design

4.2 SCIENTIFIC RATIONALE FOR STUDY DESIGN

The study design will allow the research team to address the primary objectives of assessing protocol feasibility in multiple ways (compliance, completion, and perceived burden) as well as the secondary objective of exploring personal factors (age, cognitive abilities) that relate to feasibility metrics.

4.3 JUSTIFICATION FOR INTERVENTION

N/A - This study does not involve an intervention.

4.4 END-OF-STUDY DEFINITION

The end-of-study will be at the end of the funding period (i.e., 1 year). This study is a small-scale, observational feasibility trial in which no impact on clinical outcomes is expected.

5 STUDY POPULATION

5.1 INCLUSION CRITERIA

Inclusion criteria include: (1) current/pre-stroke English proficiency, (2) normal/corrected-to-normal vision and hearing, (3) medical stability, (4) history of left hemisphere stroke at least six months prior to enrollment, and (5) presence of aphasia as determined by consideration of scores on language assessments (e.g., Quick Aphasia Battery, discourse tasks) and the study team's clinical judgment.

5.2 EXCLUSION CRITERIA

The exclusion criterion will be a history of neurological disease affecting the brain besides stroke.

5.3 LIFESTYLE CONSIDERATIONS

PWA with severe aphasia who do not have a care partner to assist with study logistics (e.g., charging smartwatches, scheduling appointments) may have more difficulty participating, but they will not be precluded from participating. PWA who have severe hemiplegia or hemiparesis may also have more difficulty participating, but accommodations (e.g., use of stretch wristbands to ease donning the watch) will be employed.

5.4 SCREEN FAILURES

Participants who do not test as aphasic on standardized testing or who do not endorse language challenges consistent with aphasia will be ineligible to participate.

5.5 STRATEGIES FOR RECRUITMENT AND RETENTION

[name] has a strong foothold in the Boston aphasia research community due to her time at Boston University as a PhD student and has several existing and developing collaborations at area institutions that will offer ample opportunities for recruitment for this study. Although the final sample for this pilot study is small, a multipronged approach will be implemented to ensure recruitment goals are met.

Specifically, recruitment at the following sites and via the following methods will be launched in parallel at the beginning of the project and will continue until the project's end and/or until recruitment goals are achieved:

Northeastern University Speech, Language, and Hearing Center (SLHC): The Northeastern University SLHC provides clinical SLP and audiology services to individuals across the lifespan with communication disorders. Led by [name], the Aphasia Workshop is a new program offered through the SLHC in which PWA complete a one-time assessment of speech and language skills. Each academic semester, up to five PWA participate in this program. [name] has agreed to share study flyers with new participants each semester and to email previous Aphasia Workshop attendees. [name] is also the coordinator of adult SLP practicum placements for graduate students in the Communication Sciences and Disorders Department at Northeastern and has contacts with several SLPs working in the greater Boston area. [name] has agreed to email area SLPs with information about TAN Lab and the proposed study.

Boston University (BU) Aphasia Research Laboratory: Directed by [name], the BU Aphasia Research Lab maintains a database of nearly 300 PWA. [name] has agreed to share study flyers with the many PWA currently active in her research lab and allow TAN Lab study team members to speak directly to interested PWA following their sessions at the BU Aphasia Research Lab. The BU Aphasia Lab manager will also follow up with PWA who agreed to be contacted for future research opportunities and will provide interested PWA the contact information for TAN Lab.

Other Recruitment Methods: We will recruit stroke survivors via flyers placed at local hospitals, senior centers, and clinics that serve individuals with neurogenic disorders. We will also develop and implement a pipeline for recruiting stroke survivors through Tufts Medical Center that will be initiated following a meeting with the Tufts Recruitment and Retention Team. Finally, we will present at the Boston University Aphasia Community Group in April 2022 (established via personal communication between [name] and [name], the clinical director of the BU Aphasia Resource Center). The Aphasia Community Group is held one Saturday per month and regularly welcomes up to 100 PWA and their family/friends.

When possible, TAN Lab study team members will take advantage of "the clinical moment" that occurs with face-to-face interactions with patients at community engagement events and via one-on-one clinical research encounters. The goal of these interactions will not solely be to inform potential participants of the present study but to engage PWA in the research process, convey the larger goals of TAN Lab, and describe our work towards maximizing outcomes for PWA. [name] and TAN Lab SLP graduate student RAs will utilize their clinical aphasia expertise and collaborate with the Tufts CTSI Recruitment and Retention Team to develop effective externally facing materials for engaging potential participants. Written recruitment materials and in-person communications will incorporate aphasia-friendly language (simple language, short phrases) and multimodal auditory-visual strategies to aid comprehension for PWA with severe language deficits. Working with the Tufts CTSI Recruitment and

Version 1.000

Protocol 15 March 2022

Retention Team, we will also develop and implement strategies to ensure recruitment of participants of color. One strategy will be to maximize engagement with Hispanic/Latinx and Asian PWA involved in an active clinical trial conducted by the BU Aphasia Research Lab on bilingual aphasia recovery. Given our multipronged approach, the large pool of potential participants, and expected high interest in the study, we anticipate having a waitlist of potential participants. Thus, a second approach will be to prioritize participation of PWA of color on the waitlist to ensure their necessary inclusion in this study. All efforts will be made to maximize retention of enrolled participants. We will do so by: (1) careful screening of potential participants in which we explain in detail the procedures (e.g., protocols, time commitment) and provide time and opportunity for addressing the questions/concerns of participants and/or care providers, (2) providing flexible scheduling options and assistance with arranging transportation as needed, and (3) weekly contacts in weeks 2-4 during the EMA/μEMA protocols with PWA and/or their care providers.

6 STUDY INTERVENTION(S) OR EXPERIMENTAL MANIPULATION(S)

6.1 STUDY INTERVENTION(S) OR EXPERIMENTAL MANIPULATION(S) ADMINISTRATION

6.1.1 STUDY INTERVENTION OR EXPERIMENTAL MANIPULATION DESCRIPTION

Participants will be pseudo-randomly assigned to either the 1-item EMA condition (n = 10) or 9-item EMA condition (n = 10). For every prompt, the smartwatch will vibrate to alert the participant to a prompt to complete either a single picture naming trial (in the 1-item condition) or a set of picture naming trials (in the 9-item EMA condition). Participants in both conditions will be scheduled to complete 36 overt picture naming trials per day for three weeks. The only difference between conditions will be the trial delivery schedule: PWA in the 1-item condition will complete a single naming trial at a time, 36 times per day whereas PWA in the 9-item EMA condition will receive four prompts per day to complete a set of nine picture naming trials per prompt. The twofold rationale for comparing 1-item and 9-item EMA conditions is that we will be able to ensure the results reflect the viability of either delivery schedule specifically and not just the novelty of smartwatch use, and this approach will provide preliminary data regarding which method works best for which PWA.

6.1.2 ADMINISTRATION AND/OR DOSING

In each condition, the smartwatch will vibrate to alert PWA to a single naming trial (1-item condition) or naming trial set (9-item EMA condition). After the vibration alert, PWA will see a screen that says "Ready to name a picture?" (1-item condition) or "Ready to name some pictures?" (9-item EMA condition). If the participant taps YES, a picture will appear, and the device will begin recording audio. PWA will have up to five seconds to provide an oral response, after which a "Thanks!" screen will appear. The fivesecond response window was selected based on research showing that PWA correctly name pictures within 3.5 seconds, on average, with longer response latencies for incorrect responses. If a participant fails to respond to a vibration prompt or pushes the NO button to the "Ready?" screen, they will be reprompted five minutes later via one more vibration alert. During the three-week EMA protocol, each participant will attempt to name 108 unique objects derived from the 260-item Snodgrass and Vanderwart photoset. The subset of pictures presented to each participant will be based on their naming evaluation (during week 1, session 1). When possible, half of the pictures will be items the PWA named correctly during the evaluation, and the other half will be incorrectly named pictures. This approach will allow us to gauge naming variability over time of items PWA are able versus unable to name during traditional SLP assessment, providing an important window into anomia. To mitigate practice effects, the individual pictures (1-item condition) or picture sets (9-item EMA condition) will be presented randomly without replacement until all 108 pictures have been presented, and then the picture cycle will restart. In both conditions, 36 naming trials will be scheduled per day, resulting in a total of 756 scheduled trials for each participant across the experiment. In the 1-item EMA condition, single-naming trial prompts will appear at random intervals from 10am to 8pm. In the 9-item EMA condition, PWA will receive four prompts per day to complete a set of nine picture naming trials per prompt; one prompt will be scheduled in every 2.5-hour block between 10am and 8pm.

15 March 2022

6.2 FIDELITY

Protocol

6.2.1 INTERVENTIONIST TRAINING AND TRACKING

N/A - There is no intervention as part of this trial. Data used to calculate compliance, completion, and perceived burden will be automatically digitally recorded. Speech intelligibility ratings will be completed for all samples by one rater, and 20% of samples will be assessed by a second rater.

6.3 MEASURES TO MINIMIZE BIAS: RANDOMIZATION AND BLINDING

PWA will be pseudo-randomly assigned to either the 1-item or 9-item EMA condition. This quasi-randomization will be done to ensure the conditions are balanced for overall aphasia severity. No blinding will be performed.

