8.1 ENDPOINT AND OTHER NON-SAFETY ASSESSMENTS

Endpoint Assessments: Feasibility will be classified in three ways: (1) PWAs' adherence to the smartwatch μΕΜΑ or EMA protocol via compliance and completion, (2) PWAs' perceived burden of completing the EMA protocol, and (3) speech intelligibility of recorded naming attempts. Currently, PWAs' capacity for adhering to a smartwatch EMA protocol via button press responses or verbal responses is unknown. As such, compliance will be based on the number of YES button responses to the "Ready?" screen whereas completion will be based on naming attempts. Specifically, similar to [name] et al. (2016), compliance will be determined by the number of YES responses over scheduled trials, including trials missed due to the watch being off/uncharged. Completion will be calculated as trials with captured audio (reflecting attempted naming) over delivered trials, excluding trials missed to the watch being off/uncharged. Perceived burden will be measured via responses to the weekly surveys during weeks 2-4. Finally, speech intelligibility will be measured by a categorical rating of responses captured in each audio clip (i.e., completely intelligible, partially intelligible, or completely unintelligible).

Other Non-Safety Assessments: Before the EMA period, PWA will be administered the following testing battery. The Quick Aphasia Battery (QAB) will be used as our eligibility assessment and to measure overall aphasia severity. The Pattern Comparison Processing Speed Test and Flanker Inhibitory Control and Attention Test from the NIH Cognition Toolbox will be used to measure non-linguistic visual attention and executive functions, respectively. We will use brief, standardized picture description and story elicitation tasks from the AphasiaBank protocol to index anomia in discourse. Participants will complete an overt object naming test twice before EMA and once after EMA so that the research team can evaluate word retrieval via the standard SLP assessment format (i.e., single administration in a quiet 1:1 interaction). This picture naming probe will include normed real photos of the 260 items from the Snodgrass and Vanderwart stimuli set. Before EMA, PWA will also participate in an intake interview and complete a questionnaire about their comfort with technology, adapted for aphasia (simple language, short phrases).

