9.4.2 ANALYSIS OF THE PRIMARY ENDPOINT(S)

We will code each trial in the EMA time series to index compliance, completion, and speech intelligibility. Every scheduled trial (n = 756 total trials) will be coded as 0 for a nonresponse/ NO button

Version 1.000

Protocol 15 March 2022

response or 1 for a YES button response, reflecting compliance. Every delivered trial with a naming attempt captured on audio (n trials will vary by person) will be coded as 0 for incomplete or 1 for complete, reflecting completion. For each of these measures, we will run a logistic mixed effects model with one of the feasibility measures (i.e., compliance, completion) as the dependent variable, condition (1-item vs. 9-item) as the independent variable, and random effects of participant and trial.

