9.4.3 ANALYSIS OF THE SECONDARY ENDPOINT(S)

Every audio clip (n trials will vary by person, depending on the number of naming attempts) will be coded as 0 for completely or partially unintelligible and 1 for completely intelligible, reflecting speech intelligibility. We will run a logistic mixed effects model with intelligibility as the dependent variable, condition (1-item vs. 9-item) as the independent variable, and random effects of participant and trial. For perceived burden, we will collect responses on three questions/survey for three weeks. Given the small amount of data, survey responses will be plotted to visualize trends in increasing/decreasing burden rather than compared statistically. We will statistically compared averaged burden ratings between participants in the 1-item vs. 9-item condition using t-tests or Wilcoxon rank sum tests (depending on the distribution of the data).

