9.4.9 EXPLORATORY ANALYSES

We will conduct a series of partial correlations between patient-specific factors and feasibility measures (compliance, completion, speech intelligibility, and perceived burden), controlling for study condition. Patient-specific factors will include age, aphasia severity (derived from the QAB), non-linguistic cognitive skills (averaged performance on the two NIH Toolbox tasks), and a summary score derived from the

Version 1.000

Protocol 15 March 2022

comfort with technology survey. Here, compliance will be the proportion of YES button responses divided by total scheduled trials (YESbutton/756) for each participant. Completion will be the proportion of naming attempts divided by total delivered trials (n naming attempts/n trials delivered). Speech intelligibility will be the proportion of completely intelligible responses divided by the total number of naming attempts (n completely intelligible trials/n naming attempts). Perceived burden will be calculated as the sum of all burden question Likert responses. Multiple comparison correction will be done at a false discovery rate of p < 0.05.

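### Assignment is balanced on aphasia severity but the mixed models leave it out, which costs precision to the extent that severity predicts the outcome

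*Combined protocol and SAP*

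**What the plan says.** The synopsis (1.1) states that "PWA will be pseudorandomly assigned to either the 1-item or 9-item EMA condition, counterbalanced for aphasia severity", and section 6.3 gives the reason: "This quasi-randomization will be done to ensure the conditions are balanced for overall aphasia severity". Section 6.1.1 sets 10 participants per condition.

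Section 9.4.2 specifies logistic mixed models for compliance and completion with "condition (1-item vs. 9-item) as the independent variable, and random effects of participant and trial". Section 9.4.3 uses the same structure for intelligibility: a "logistic mixed effects model with intelligibility as the dependent variable, condition (1-item vs. 9-item) as the independent variable", again with random participant and trial effects. None of the three models has a severity term.

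The score is available on everyone before the EMA period. Section 8.1 says "The Quick Aphasia Battery (QAB) will be used as our eligibility assessment and to measure overall aphasia severity". In the analysis, severity appears only in the baseline description (9.4.5) and as one of four factors in the exploratory partial correlations (9.4.9). Those correlations control for condition. They do not adjust the condition comparison for severity.

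**The concern.** Condition varies between participants, so with 10 per arm the spread between participants governs the precision of the comparison hypothesised in 9.1. The 756 trials per person do little to reduce that part of the variance.

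Balancing on a predictive baseline factor makes the arms more alike, so the estimated difference varies less from one trial to another. The analysis gets credit for this only if the factor is in the model. A random participant effect does not take its place: it carries severity as unexplained variance, and that variance enters the standard error of condition. The reported standard error then exceeds the true sampling variability, the test rejects less often than its nominal 5%, and power that the design has already secured is given away.

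**Working it through.** **The plan's own figure.** Section 9.2 states 80% power for an odds ratio of 1.20 with 756 repeated measures, AR(1) correlation 0.600, 10 per group, alpha 0.05 and reference proportion 0.500.
- Design effect for the mean of 756 AR(1) observations: 3.99.
- Effective trials per group: 10 × 756 / 3.99 ≈ 1,895.
- Comparison proportion: 1.2 / 2.2 = 0.5455.
- SE of the log odds ratio: √[1/(1,895 × 0.25) + 1/(1,895 × 0.5455 × 0.4545)] = 0.0651.
- Two-sided power: 79.96%.

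The figure reproduces. However, AR(1) correlation dies away, so this calculation contains no lasting difference between participants and severity has nothing to explain in it. The random participant effect planned in 9.4.2 does allow for such differences, so the checks below include them.

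**Assumptions.** The documents give neither the between-participant spread nor the share of it that severity explains (R²), so both are assumed over a range.

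**Step 1: expected size.** If balancing is good, adjustment divides the SE by about 1/√(1 − R²). This is 1.00, 1.05, 1.20 and 1.29 at R² = 0, 0.1, 0.3 and 0.4.

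**Step 2: participant-level simulation.** Assumed participant SD 0.20 in the proportion, true difference 0.20; 20,000 trials per cell; two-sample t test (18 df) against analysis of covariance on severity (17 df).

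| R² | SE ratio, pairs | Power without v with, pairs | Type I without, pairs | Power without v with, two strata | Type I without, two strata |
|---|---|---|---|---|---|
| 0 | 1.00 | 57 v 57% | 5.1% | 56 v 55% | 4.8% |
| 0.1 | 1.06 | 57 v 60% | 4.2% | 56 v 59% | 4.2% |
| 0.3 | 1.20 | 57 v 71% | 2.4% | 56 v 70% | 3.0% |
| 0.4 | 1.30 | 57 v 78% | 1.6% | 57 v 77% | 2.5% |

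Type I error of the adjusted test under matched pairs is 4.9–5.1%. A fresh run agreed with this table to within about 1 point.

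**Step 3: logit scale, closed form.** SE² = (2/10) × [σ²(1 − R²) + w], where σ is the between-participant SD on the logit scale and w = 3.99 / (756 × 0.25) = 0.021 is the within-participant variance. Take σ = 1.0 and 0.50 v 0.70, a log odds ratio of 0.847.
- Without severity: SE = √(0.2 × 1.021) = 0.452 and 0.847 / 0.452 = 1.87, giving 42.7% power on 18 df.
- With severity at R² = 0.3: SE = √(0.2 × 0.721) = 0.380 and 0.847 / 0.380 = 2.23, giving 55.7% power on 17 df.
- With severity at R² = 0 and 0.1: 42.4% and 46.1%.

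**Step 4: logistic random-intercept model.** 756 trials, matched pairs, 0.50 v 0.70, σ = 1.0, 2,000 trials per cell; t reference with the SE scaled up for 20 participants. Power without v with severity is 42 v 42, 42 v 46, 41 v 56 and 40 v 62% at R² = 0, 0.1, 0.3 and 0.4. At σ = 0.5 the unadjusted model already has 94–97% power and the gain is at most about 3 points.

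A separate simulation of 400 runs per cell shows the mechanism at R² = 0.3. The mean reported SE without severity is 0.431, while that estimate's actual sampling SD is 0.403. With severity the mean reported SE is 0.349. The estimated effect hardly moves (0.866 v 0.861).

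**Step 5: inference method.** With Wald z, the adjusted logistic model has type I error of 8.3–9.7% in all the Step 4 scenarios. In the 400-run simulation, a t reference without any SE correction still gave 6–9%. The covariate therefore needs small-sample inference to go with it.

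The random trial effect was left out of the logistic simulations. Simulation error in the 2,000-trial runs is about 1 point for type I error and 2 points for power.

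**The case against.** The strongest reply is that the plan contains no error here. The unadjusted estimate is unbiased, its test does not inflate false positives under t inference, and the gain depends on two quantities that the documents do not give. This is correct, and the point is conditional for that reason. At R² = 0.1 the gain is 3–4 points; double-digit gains need R² of about 0.3 or more and a wide spread between participants.

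A sharper reply is that the plan names no inference method and might use Wald z. In a simulation with two strata, σ = 1.0 and 0.50 v 0.70, unadjusted Wald z had power of 53/52/51/51% at R² = 0/0.1/0.3/0.4. The adjusted t analysis had 43/46/55/62%. On that comparison the gain is only about 4 points at R² = 0.3 and is negative at low R². But unadjusted z reaches its power at low R² with type I error of 8.3% and 7.2%, so that advantage is not legitimate. Compared on the same inferential footing, the gain stands.

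It is also fair that matched pairs over all 20 participants is an extreme form of balancing, since recruitment is spread over time (5.5). The two-strata results are close, so the conclusion does not hang on pairs.

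Finally, this is a feasibility pilot. Even so, 9.1 states a formal hypothesis of a significant difference, and the documents give some reason to expect an association. Section 5.3 expects people with severe aphasia and no care partner to have more difficulty with logistics such as charging the watch, and 8.1 counts trials missed because the watch was off or uncharged against compliance.

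**Conclusion.** The concern holds in its conditional form: the three models omit the factor on which assignment is balanced, and precision is lost to the extent that this factor predicts the outcome. On the assumed values, the unadjusted SE is 1.06 times the adjusted one at R² = 0.1, 1.20 times at 0.3 and 1.30 times at 0.4. With the wider participant spreads (SD 0.20 in the proportion, or 1.0 on the logit scale), the power cost is about 3–4 points at R² = 0.1 and about 14–15 points at R² = 0.3. It is nil at R² = 0 and small where participants differ little (logit SD 0.5).

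Two limits apply. For intelligibility the hypothesis in 9.1 is a level (over 80%), so only the condition contrast in 9.4.3 is affected. And adjustment does not rescue 9.2: with lasting between-participant variance (logit SD 0.5 to 1.5), power for an odds ratio of 1.20 is 5.8–11.5% without severity and 5.8–17.2% with it, for R² up to 0.5. That is a separate and larger issue. The change should be made, with medium confidence in how much it will gain.

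**What to change.** - In 9.4.2 (compliance, completion) and 9.4.3 (intelligibility), pre-specify the baseline QAB overall score as a continuous fixed effect alongside condition.
- State the inference method in place of Wald z: a t reference with participant-level degrees of freedom and a small-sample-corrected SE, a parametric bootstrap, or a permutation test that respects the balancing. The permutation option requires 6.3 to state the balancing rule.
- Keep the unadjusted model as a sensitivity analysis.

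The cost is one participant-level degree of freedom per model (about 1 point of power or less if severity is unrelated to the outcome) and a sentence on inference, plus the balancing rule in 6.3 if permutation is chosen. No new data or staff are needed.
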